## 11.3 Evaluation of Study Endpoints

### 11.3.1 Evaluation of the Primary and Secondary Endpoints

Overall response rate (ORR) will be evaluated at 24 and 48 weeks after combination therapy (i.e. 28 and 52 weeks after enrollment), respectively. The proportion of responders and its 95% confidence interval (using exact binomial methods) will be calculated.

Failure-free survival (FFS) will be evaluated using Kaplan-Meier method. The FFS rate will be evaluated at 24 and 48 weeks after combination therapy (i.e. 28 and 52 weeks after enrollment), The composite endpoint of failure is defined as 1) GvHD progression or loss of response requiring switch of systemic GvHD treatment, 2) relapse of primary hematologic disease and 3) non-relapse mortality.

Durable response after response achievement will be evaluated only in the patients achieved CR or PR (any response). The Kaplan-Meier estimate will be calculated from the date of CR/PR achievement to the date of losing response/progression or death from any cause.

GvHD symptom burden improvement, measured serially by the modified Lee Symptom Scale, will be evaluated using repeated measure based on the general linear model. If p-value is less than 0.05, it demonstrates statistically significant change over time within subject.

The Modified Lee symptom score (mLSS) will be used to reflect a symptom burden in cGvHD study patients. The symptoms will be assessed serially and will be evaluated using repeated measure based on the general linear model. If p-value is less than 0.05, it demonstrates statistically significant change over time within subject. The score assesses 7 different organs/areas including skin, eye/mouth, breathing, eating/digestion, muscle/joints, energy, and mental/emotional health. The sum of these domains will be calculated to derive the total mLSS. Clinically meaningful improvement in mLSS is defined as a reduction of  $\geq 7$  points in overall mLSS. Longitudinal change in mLSS is analyzed by repeated measures using generalized linear model over time, evaluating within-subject and between-subject effects. In addition, the proportion of the patients showing clinically meaningful improvement in mLSS is analyzed longitudinally at 12, 24, and 48 weeks. In addition, the best improvement in mLSS is also calculated in each subject and plotted.

Safety and tolerability (primary endpoint) will be assessed throughout the treatment duration using CTCAE v5.0 grading. Adverse events will be summarized descriptively, including: - Incidence (number and percentage) of AEs, SAEs, and AESIs by grade, system organ class, preferred term, and relationship to study drug (belumosudil, ruxolitinib, or combination). - Frequencies and percentages for AEs leading to dose modifications, interruptions, or discontinuations. - Time-to-first AE (for key events) using Kaplan-Meier estimates if appropriate. No formal hypothesis testing will be performed for safety; results will be presented in tabular and graphical formats.

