## **2. STUDY DESIGN**

This is a phase II non-randomized, open-label study in patients with moderate to severe cGvHD who have failed to respond to, or are intolerant of first line therapy. Patients will receive combination therapy with two oral agents (belumosudil, ruxolitinib) with documented individual efficacy as second line in cGVHD treatment. A maximum of 63 participants are expected to be enrolled in Canada.

[figure not shown]
Participants will begin on 10 mg BID of oral ruxolitinib alone for one cycle (i.e. Cycle 1). Each cycle is equal to 28 days. Starting at cycle 2, they will take belumosudil in addition to ruxolitinib, at a dose of 200 mg OD or 200 mg BID (if on a PPI). Patients will remain on dual therapy for 48 weeks (i.e. 12 cycles), until progression of cGVHD, or intolerance to either agent, whichever occurs sooner. A safety visit will be conducted at the end of treatment, 28 days following end of treatment, as well as a remote follow up visit conducted 24 weeks following end of treatment.

The end points will include overall response rates at 24 weeks on treatment and failure-free survival at 48 weeks on treatment (i.e., 28 and 52 weeks on combination therapy) which adopts composite endpoints including: (1) requirement of additional treatment or switch over, (2) progression or flare-up of GvHD with/without ruxolitinib tapering, and (3) death from relapse/non-relapse mortality.

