**Figure 1. Participant treatment schema**

## 3. OBJECTIVES

Primary Objectives	Primary Endpoints
To evaluate efficacy, tolerability and safety of combination treatment of belumosudil with ruxolitinib as second line therapy for steroid-refractory cGvHD.	
 
Efficacy will be assessed using overall response rate (ORR) as per the NIH cGvHD Consensus Response Criteria at 24 weeks of combination treatment (C8D1) of belumosudil with ruxolitinib (i.e., 28 weeks after C1D1).
 
Tolerability and safety will be assessed by the incidence and severity of adverse events (AEs) throughout the treatment duration using CTCAE v5.0 grading.
 

Secondary Objectives	Secondary Endpoints
To evaluate the response achievement with combination treatment of belumosudil with ruxolitinib as second line treatment for cGvHD.	
 
ORR as per the NIH cGvHD Consensus Response Criteria after 48 weeks of combination treatment of belumosudil with ruxolitinib (i.e., 52 weeks after C1D1).
 
Failure-free survival (FFS) after 24 and 48 weeks of combination treatment of belumosudil with ruxolitinib (i.e., 28 and 52 weeks after C1D1). FFS is defined as the time from treatment initiation until the occurrence of treatment failure.
 
Durable response rate in patients who achieve complete or partial response with combination treatment of belumosudil with ruxolitinib as assessed at 52 weeks from
 

	
C1D1. Durable response is defined as sustained improvement in symptoms or absence of disease progression from the time of treatment initiation.
 
4. Overall GvHD symptom burden improvement, serially measured with a modified Lee Symptom Scale (see Appendix D).

Exploratory Objectives	Exploratory Endpoints
To evaluate improvement in musculoskeletal involvement of sclerotic GvHD using the P-ROM score measurement.	1. Changes in the P-ROM score after 12, 24, and 48 weeks of combination therapy in patients who have developed sclerotic GvHD in musculoskeletal involvement of GvHD

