### **5.6 Premature Withdrawal/Discontinuation Criteria**

At the discretion of the QI, a patient may be removed from the study for the following reasons:

- Progression of cGVHD as defined by NIH Consensus Criteria
- Noncompliance with study procedures
- Need for treatment with medications, such as a new systemic agent for cGVHD, not allowed by the study protocol
- Recurrence of underlying malignancy, as defined by established disease specific criteria, or other intercurrent illness that interferes with study assessments

- Unacceptable toxicity related to study participation
- Investigator decision.
  - Note that patients should be withdrawn from the study if there has been no response after 12 months of treatment, if in the judgement of the Investigator there has been no clinical benefit for the patient, e.g., in terms of organ score improvements, improvements in Lee symptom scores or reductions of corticosteroid / tacrolimus doses.
- Other treatments become available
- Patient preference / withdrawal of consent or loss to follow-up
- Termination of the study by the sponsor
- Pregnancy in a female participant will lead to definitive treatment discontinuation in all cases.

Patients with a Lack of Response or Mixed response may continue treatment with belumosudil and ruxolitinib, and can remain on study if the treating Investigator considers continued treatment to be in the patient's best interest, but only after approval from the Sponsor and documentation of patient's willingness to continue. The rationale for continued treatment in such instances must be clearly documented. For clarity, Lack of Response or Mixed response will be considered as progression event for analysis purposes.

Patients may withdraw from the study at any time. Patients who discontinue from the study will be encouraged to return to the study site to undergo the evaluations listed for the End of Treatment Visit and for follow-up visits. In the instances where a reason for withdrawal of consent is given, this will be captured in the eCRF. Patient data up to withdrawal of consent will be included in the analysis of the study, and where permitted, publicly available data can be included after withdrawal of consent.

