### **7.3 Response Duration**

Response duration will be defined as the time from the first documented achievement of complete response (CR) or partial response (PR), whichever occurs first (as defined in Table 7), until the first documented date of loss of response or disease progression. The smallest measurements recorded during the study, including baseline, will serve as the reference for assessing progression.

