## 9. CONCOMITANT MEDICATIONS

All concomitant medications (including herbal or alternative medicines) taken by the patient from the time of consent through the duration of protocol therapy will be recorded in the eCRF. Initiation of new systemic cGvHD therapy will be considered a new line of treatment and as study treatment failure.

Subsequent cGvHD therapies occurring during the follow up period (24 weeks) will also be captured.

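### Durable response has no event for the start of a new systemic cGvHD therapy, although Section 9 calls that start treatment failure

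*Protocol*

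**What the plan says.** Durable response is the third secondary endpoint. Three places in the Protocol bear on when it ends.

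- Section 11.3.1 (analysis): "The Kaplan-Meier estimate will be calculated from the date of CR/PR achievement to the date of losing response/progression or death from any cause".
- Section 7.3 (response duration): from first CR or PR "until the first documented date of loss of response or disease progression". Death is not listed.
- Section 3, repeated in the Synopsis (explicit definition): "Durable response is defined as sustained improvement in symptoms or absence of disease progression from the time of treatment initiation". The clock starts at treatment initiation, not at response.

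None of them mentions a new systemic cGvHD therapy. Section 9 does: "Initiation of new systemic cGvHD therapy will be considered a new line of treatment and as study treatment failure". Section 2 also makes "requirement of additional treatment or switch over" a component of failure-free survival (FFS) in its own right. Section 5.6 lists among the reasons for removal "Need for treatment with medications, such as a new systemic agent for cGVHD, not allowed by the study protocol", but under the lead-in "At the discretion of the QI, a patient may be removed from the study for the following reasons", so removal is permitted and not required.

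**The concern.** An endpoint that describes how long a response to the combination lasts should not treat a patient as still responding after the trial's own rule has called that patient a treatment failure. CR, PR and progression in Table 7 are organ-score changes and do not depend on which drugs the patient takes. A patient in PR who starts another systemic agent stays in PR until the scores worsen, so no listed end event occurs.

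Durability matters here. Section 1.2 gives the lack of complete and lasting responses with the single agents as a reason for combining them. An estimate that leaves out some treatment failures favours the combination on that claim. The event list is fixed in the protocol text, so this is not merely a detail left to the statistical analysis plan.

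**Working it through.** **1. Event lists side by side**

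| Place | Start of clock | Loss or progression | Death | New systemic therapy |
|---|---|---|---|---|
| Section 7.3 | first CR/PR | yes | no | no |
| Section 11.3.1, durable response | CR/PR | yes | yes | no |
| Section 3 and Synopsis | treatment initiation | progression or symptoms | not stated | no |
| Section 9 | n/a | n/a | n/a | treatment failure |
| Section 2, FFS | n/a | yes | yes | yes, on its own |
| Section 11.3.1, FFS | n/a | yes, if it requires a switch | yes | only with progression or loss |

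The FFS rule in 11.3.1, "GvHD progression or loss of response requiring switch of systemic GvHD treatment", names loss of response and switch as separate things. This tells against reading a switch as being itself a loss of response.

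**2. Who falls into the gap**

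Two rules already make most rescued patients events. Section 7.3 judges progression from the smallest measurement on study, so a flare from best response counts even if the patient is still better than at C1D1. Section 5.6 counts Lack of Response or Mixed response as progression for analysis. What is left is responders who start a new systemic agent without documented worsening: in a stable PR with residual disease, or after stopping for toxicity while in PR.

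**3. What happens to them in the analysis**

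In the Section 8 calendar, NIH organ scoring stops at the End of Treatment visit; the 28-day and 6-month visits have none. Section 2.1 says patients are followed for progression for 24 weeks after that visit, but no organ scoring is scheduled then. Two routes follow:

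- The patient leaves study treatment, has no event, and would probably be censored as responding. The protocol states no censoring rule, so this is an inference.
- The patient is kept on study at the investigator's discretion, continues to be scored, and accrues response time on the new agent.

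Both push the estimate upward.

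**4. Size, on assumed rates**

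The protocol gives no durable-response figure to reproduce. Let L be the probability of loss, progression or death within the window, and N the probability of new therapy without documented loss, with independent exponential times.

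- New therapy as an event: (1 − L)(1 − N).
- Censored at new therapy: 1 − L. The overstatement is therefore (1 − L) × N.
- Ignored, with rescue holding every response: 1 − [hL/(hL + hN)] × [1 − exp(−(hL + hN))], where hL = −ln(1 − L) and hN = −ln(1 − N).

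Window of 36 weeks (week 16 to week 52), censored against event:

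| L | N = 5% | N = 10% | N = 15% | N = 20% |
|---|---|---|---|---|
| 20% (censored 80%) | 76% | 72% | 68% | 64% |
| 30% (censored 70%) | 66.5% | 63% | 59.5% | 56% |

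The overstatement runs from 0.70 × 0.05 = 3.5 points to 0.80 × 0.20 = 16 points.

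Window of 24 weeks (week 28 to week 52), all three versions:

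| L | N | Event | Censored | Ignored |
|---|---|---|---|---|
| 25% | 5% | 71.2% | 75.0% | 75.6% |
| 25% | 10% | 67.5% | 75.0% | 76.2% |
| 25% | 20% | 60.0% | 75.0% | 77.5% |
| 15% | 5% | 80.7% | 85.0% | 85.4% |
| 15% | 10% | 76.5% | 85.0% | 85.7% |
| 15% | 20% | 68.0% | 85.0% | 86.5% |

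Example for the last column, L = 25% and N = 10%: hL = 0.2877, hN = 0.1054, sum 0.3930. Then 1 − (0.2877/0.3930) × (1 − 0.675) = 1 − 0.732 × 0.325 = 0.762.

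Censoring overstates by about 4 points at N = 5% and 15 to 17 at N = 20%. Ignoring overstates by about 4 to 5 and 17 to 19.

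**The case against.** The strongest reply is that the gap is nearly empty. Patients usually need a new agent because they worsen, and the rules in Sections 7.3 and 5.6 already make worsening an event. A reader who looks only at Section 7.2, where organs are compared with C1D1, might infer that a patient can flare, be rescued and never lose response. Section 7.3 does not support that reading.

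A reader might also infer that response time on rescue therapy is generally credited to the combination. The calendar mostly prevents it: after the End of Treatment visit there is no organ scoring to credit. It needs a patient kept on study while taking an agent that Section 5.6 describes as not allowed.

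Section 9 does not say that failure ends response duration, and treatment failure is the defining term of FFS, not of durable response. Calling this a flat contradiction would go too far; it is a failure of alignment. Censoring rules may also stand in a statistical analysis plan that is not at hand.

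The size has no basis in the documents. With about 40 responders (assumed, near the success threshold of 37), 5% is two patients. A 4-point shift is then less than the standard error of an 80% estimate, √(0.8 × 0.2/40) = 6.3 points.

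All of this narrows the point but does not remove it. No passage makes new therapy an event, the remaining cases are clinically plausible, and the direction of bias does not depend on the assumed rates.

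**Conclusion.** The point holds in a limited form. The durable-response event lists omit the start of new systemic cGvHD therapy, which Section 9 calls study treatment failure. They also disagree on death and on the start of the clock. The omission affects only responders who start a new agent without documented worsening, and it acts mainly through censoring.

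The bias is upward and its size is unknown. The figure of roughly 4 to 16 points rests entirely on assumed rates of 5% to 20% new therapy without documented loss, 20% or 30% loss of response, and independent times. It should not be read as an estimate for this trial. This is a secondary, descriptive endpoint: the definition should be corrected before results are known, but the trial does not stand or fall by it.

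**What to change.** Use one event list in Sections 7.3 and 11.3.1: time from first CR or PR to the earliest of loss of response or progression, start of a new systemic cGvHD therapy, or death from any cause. State that new therapy is an event on its start date and not a censored observation, including for patients who stopped study treatment while in response.

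Align the durable-response definition in Section 3 and the Synopsis with this list and with the same starting point. The two FFS definitions, in Sections 2 and 11.3.1, should be reconciled with Section 9 in the same amendment, since the one in 11.3.1 misses the same patients.

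The cost is a few sentences. New cGvHD therapies are already recorded during treatment and through the 24-week follow-up (Section 9), so no new data are needed. The durable-response figure may come out less favourable.

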	
Analyses:
 
 
- Primary (ORR): Proportion of responders with 95% CI at 24 weeks of combination therapy.
 
- Primary (Safety/Tolerability): Incidence and severity of AEs summarized by frequency, percentage, grade (CTCAE v5.0), and relationship to study drug.
 
- Secondary (ORR at 48 weeks, FFS, Durable response): Kaplan-Meier estimates with 95% CI.
 
- Secondary (Symptom burden): Repeated measures analysis using general linear model (<math>p < 0.05</math> for significance).
 
- Exploratory (P-ROM changes): Descriptive summaries of changes at 12, 24 and 48 weeks.
 
 
Descriptive statistics (frequencies/percentages for categorical; mean/SE/median for continuous) will be used.
 
The final analysis will be performed once all participants have either completed at least 52 weeks of treatment or discontinued study treatment prior to Week 52. Data from all participating centers will be pooled. Demographic and baseline characteristics will be summarized descriptively (frequencies/percentages for categorical variables; mean/SD/median/min-max/25th-75th percentiles for continuous). Graphical summaries may be used.
 
Dose modifications will be summarized by frequency, percentage, and reason. All tests will use a two-sided <math>\alpha = 0.05</math> unless specified. Exploratory analyses may be added as appropriate. No interim analyses are planned.
 
Study populations are defined in 11.2. Endpoint evaluations are detailed in 11.3, including: - Proportions with 95% CI for binary outcomes (e.g., ORR). - Kaplan-Meier method for time-to-event outcomes (e.g., FFS, durable response). - Repeated measures using general linear model for longitudinal data (e.g., symptom burden). - Descriptive statistics for changes in exploratory measures (e.g., P-ROM scores).

--	--

---

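### The only stated test of symptom burden (mLSS) is a non-directional change-over-time p-value for an endpoint worded as improvement; a named mixed-model contrast would match the endpoint and use all observed visits

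*Protocol*

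**What the plan says.** The endpoint is directional. Protocol section 3 lists as secondary endpoint 4: "Overall GvHD symptom burden improvement, serially measured with a modified Lee Symptom Scale".

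The test is not. Section 11.3.1 says the mLSS "will be evaluated using repeated measure based on the general linear model", and adds: "If p-value is less than 0.05, it demonstrates statistically significant change over time within subject". Both statements appear twice in that section. The Synopsis repeats the method ("Repeated measures analysis using general linear model") and the 0.05 threshold.

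Later in section 11.3.1 the longitudinal change is "analyzed by repeated measures using generalized linear model over time, evaluating within-subject and between-subject effects". The trial has one arm and the section names no between-subject factor.

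The section also contains directional summaries. "Clinically meaningful improvement in mLSS is defined as a reduction of" at least 7 points, "the proportion of the patients showing clinically meaningful improvement in mLSS is analyzed longitudinally at 12, 24, and 48 weeks", and each patient's best improvement is plotted.

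The Study Calendar (section 8) schedules the mLSS at weeks 0, 4, 8, 16, 28, 40 and 52 and at the end-of-treatment visit. Section 2 ends treatment early at progression of cGvHD or intolerance to either agent. Section 11.3.1 does not say how missing visits enter the model.

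**The concern.** Three things in the stated analysis do not fit the endpoint.

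- **Direction.** A time effect across seven visits asks whether the visit means are all equal. It cannot distinguish a fall from a rise, or a lasting change from one that has gone by the 24-week assessment. It yields no estimate to set beside the protocol's 7-point threshold.
- **Model.** General and generalized linear models are different classes, and their repeated-measures forms treat missing visits differently. The text does not settle which is meant.
- **Selection.** The classical repeated-measures general linear model, as software usually runs it, drops any patient with a missing visit. Treatment stops at progression or intolerance, so late scores are likely to be missing more often in patients doing badly, and completers would look better than the cohort.

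At stake is the interpretation of a patient-reported secondary endpoint. The trial's success rule is not affected: it rests on ORR alone (section 11.1).

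**Working it through.** The protocol gives no SD, power or sample size for the mLSS, so there is no figure of its own to reproduce.

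**Inputs from the protocol:** 63 enrolled (Synopsis; section 11.1); 7 on-treatment mLSS visits (section 8); p<0.05 and the 7-point reduction (section 11.3.1). The only dropout figure, 10%, was set for the 6-month ORR (section 11.1).

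**Assumptions:** SD 15 at each visit; correlation 0.5 + 0.5 × 0.5^lag, that is 0.75 between adjacent visits and about 0.51 between first and last; discontinuation by week 52 of 10, 25, 40 or 55%. Non-zero effects build up over the first visits and then hold, except for the transient case in step 2. Where dropout depends on worsening, its log-odds rise by 0.5 for each 10-point increase from baseline. There were 800 to 1,500 simulated trials per setting.

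**Methods compared:** (a) the omnibus time test in patients with all 7 visits, as a multivariate test and as a univariate F test with Greenhouse-Geisser correction, which gives the two ends of each range below; (b) a likelihood model with unstructured covariance on all observed visits, testing week 28 (C8D1) minus week 0 (C1D1).

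**Step 1: direction, complete data.** Proportion of runs with omnibus p<0.05:

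| True change | Omnibus p<0.05 |
|---|---|
| -7 (improvement) | 0.92-0.96 |
| +7 (worsening) | 0.91-0.97 |

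The lack of direction belongs to the test and does not depend on the assumed SD.

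**Step 2: transient change.** For a 7-point change back at zero by week 28, with 25% discontinuation driven by observed worsening, p<0.05 occurs in 0.99-1.00 of runs if the change was an improvement and 0.96-0.98 if it was a worsening. The week-28 contrast is significant in about 2% of runs in each direction, as it should be.

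**Step 3: patients left for a complete-case analysis.** With random dropout, 63 × (1 - d) gives 63 × 0.90 = 56.7, 63 × 0.75 = 47.3, 63 × 0.60 = 37.8 and 63 × 0.45 = 28.4. Isolated missed visits would lower these further.

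**Step 4: power for a true -7 change, random dropout.**

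| Discontinuation | Complete-case omnibus | Mixed-model contrast (improvement) |
|---|---|---|
| 10% | 0.88-0.95 | 0.96 |
| 25% | 0.78-0.89 | 0.94 |
| 40% | 0.64-0.77 | 0.89 |
| 55% | 0.47-0.65 | 0.85 |

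**Step 5: no true change, dropout driven by observed worsening.** Estimated change from week 0 to week 28:

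| Discontinuation | Complete-case estimate | Complete-case omnibus p<0.05 |
|---|---|---|
| 10% | -0.9 | 5% |
| 25% | -1.8 | 8-10% |
| 40% | -2.9 | 11-14% |
| 55% | -4.2 | 17-20% |

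The mixed-model estimate lies between -0.2 and +0.1 throughout. The same selection can also hide harm: with a true 5-point worsening and 55% discontinuation, the complete-case estimate is +0.2 and the mixed-model estimate +5.0.

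**Step 6: no true change, dropout driven by worsening not yet recorded.** Both methods are biased. At 10, 25 and 40% the mixed model gives -0.2, -0.6 and -1.1, and complete cases give -0.8, -2.1 and -3.4.

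**The case against.** The strongest reply is that much of this is detail for a statistical analysis plan that is not shown. Missing visits, covariance structure and contrasts are often settled there, and their absence from a protocol is not a fault. That stands as far as it goes. The point here is what the protocol does fix: a named model and a p<0.05 reading that do not answer the endpoint, and two model names that disagree.

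Some stronger readings are tempting but unsupported:

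- *The protocol analyses only patients with every visit.* It does not say so. That is how the classical model is usually run, and a generalized model for repeated measures can use all observed visits.
- *The plan cannot show improvement.* Only the omnibus p-value lacks direction. The 7-point responder proportions and best-improvement plots are directional, although they carry no stated test.
- *A p-value below 0.05 would be claimed as benefit.* Section 11.3.1 claims only change.
- *Unanswered items count as zero and so inflate improvement.* The section says "The sum of these domains will be calculated to derive the total mLSS" and nothing about blanks. A blank at baseline would work the other way.

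Selection may also be milder than in the simulation. The mLSS is collected at end of treatment, patients who discontinue are encouraged to attend that visit, and patients with a lack of response or a mixed response may stay on treatment with sponsor approval (section 5.6). At 10% discontinuation the two methods differ little.

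Nor is the mixed model free of cost: it assumes data missing at random, and an unstructured covariance over 7 visits has 7 × 8 / 2 = 28 parameters for at most 63 patients.

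**Conclusion.** The concern holds in a limited form and should be corrected. The one stated mLSS test is non-directional while the endpoint is improvement; this follows from the text and needs no assumption. The inconsistent model name is likewise plain in section 11.3.1.

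The selection problem is conditional. It arises if the model is run in its usual complete-case form, and its size depends on the assumed SD, correlation and dropout mechanism. Under the assumptions above the bias runs from about -0.9 points at 10% discontinuation to -4.2 at 55%, the latter being more than half of the protocol's 7-point threshold. A likelihood mixed model removes it when dropout depends on observed scores, and only reduces it when dropout depends on unobserved ones.

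Neither analysis can attribute a change to the combination: there is no control arm, and the C1D1 baseline precedes a cycle of ruxolitinib alone.

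**What to change.** In section 11.3.1 and the Synopsis:

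1. Name one model throughout: a likelihood-based mixed model for repeated measures on all observed mLSS visits, with visit as a category. Specify an unstructured covariance with a simpler fallback if it does not converge. Remove the reference to between-subject effects, or name the factor meant.
2. Replace the change-over-time rule with the C8D1-minus-C1D1 contrast (24 weeks of combination), reported with estimate and 95% CI and read against the 7-point reduction. Make C13D28 minus C1D1 supportive.
3. Keep the responder proportions and best-improvement plots, and state the denominator of the proportions.
4. Add a sensitivity analysis for missing visits in which patients who stop are allowed to have worse unobserved scores.

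The cost is analysis wording and some extra programming, with no new patients, visits or data. The downsides are the missing-at-random assumption, which item 4 probes, and the need to commit to a time point and a covariance structure before the data are seen.
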